6.2. Exclusion Criteria

Subjects will be excluded from study enrollment if they meet any of the following criteria at screening and/or Day -1:

- [7] are investigative site personnel directly affiliated with this study and their immediate families. Immediate family is defined as a spouse, biological or legal guardian, child, or sibling
- [8] are employees of Eli Lilly and Company (Lilly), Covance, or a third-party organization involved in the study
- [9] are currently enrolled in a clinical study involving an investigational product (IP) or any other type of medical research judged not to be scientifically or medically compatible with this study
- [10] have participated, within the last 30 days in a clinical study involving an IP. If the previous IP has a long half-life, 5 half-lives or 30 days (whichever is longer) should have passed
- [11] have previously completed or withdrawn from this study or any other study investigating ixekizumab, and have previously received the IP or have been administered other anti-IL-17 agents
- [12] have known allergies to ixekizumab, related compounds or any components of the formulation, or history of significant atopy
- [13] have self-perceived dullness or loss of sensation on either side of their arm, thigh, or abdomen
- [14] have uncontrolled arterial hypertension characterized by a systolic blood pressure >160 mmHg or diastolic blood pressure >100 mmHg

Note: if an initial blood pressure reading exceeds this limit, the reading may be repeated once after the subject has rested sitting for ≥ 10 minutes. If the repeat value is less than the criterion limits, the second value may be accepted.

- [15] have a significant history of, or current cardiovascular, respiratory, hepatic, renal, gastrointestinal, endocrine, or hematologic disorders, that in the opinion of the investigator poses an unacceptable risk to the subject if participating in the study or of interfering with the interpretation of data
- [16] have presence of significant uncontrolled neuropsychiatric disorder; have lifetime history of suicidal behavior (yes to any suicidal behavior question from the "Suicidal Behavior" portion of the C-SSRS from screening and between screening and baseline [Day -1]); have history of active suicidal ideation within the past year (yes to question 4 or 5 on the "Suicidal Ideation" portion of the C-SSRS from screening and between screening and baseline [Day -1]); and/or are clinically judged by the investigator to be at risk for suicide
- [17] have recent history (past 30 days) of depression; have Hospital Anxiety Depression Scale (HADS) Depression subscale score of ≥ 11
- [18] have current or history of inflammatory bowel disease (IBD) (Crohn's disease or ulcerative colitis), signs or symptoms indicative of ulcerative colitis or Crohn's disease (based on investigator determination), or knowledge of a family history of IBD in first degree relatives
- [19] Infections:
 - [19a] have had a serious infection (e.g., pneumonia, cellulitis, and sepsis), have been hospitalized, or have received intravenous antibiotics for an infection within 12 weeks prior to Day 1; have had a serious bone or joint infection within 24 weeks prior to Day 1, or have ever had an infection of an artificial joint; or are immunocompromised to an extent such that participation in the study would pose an unacceptable risk to the subject
 - [19b] have or have had an infection typical of an immunocompromised host and/or that occurs with increased incidence in an immunocompromised host (including, but not limited to, pneumocystis jiroveci pneumonia, histoplasmosis, or coccidioidomycosis), or have a known immunodeficiency
 - [19c] have or have had a herpes zoster infection or any other clinically apparent varicella-zoster virus infection within 12 weeks of Day 1
 - [19d] have had any other active or recent infection within 4 weeks of Day 1 that, in the opinion of the investigator, would pose an unacceptable risk to the subject if participating in the study; these subjects may be rescreened (once) ≥ 4 weeks after documented resolution of symptoms

[20] have a history of uncompensated heart failure, fluid overload, or myocardial infarction, or evidence of new-onset ischemic heart disease or other serious cardiac disease, within 12 weeks prior to Day 1

[21] have clinical laboratory test results at screening that are outside the normal reference range for the population and are considered clinically significant, and/or have any of the following specific abnormalities:

- neutrophil count <1500 cells/ μ L
- lymphocyte count <800 cells/ μ L
- platelet count <100,000 cells/ μ L
- total white blood cell count <3000 cells/ μ L

Note: Screening and/or Day -1 laboratory testing may be repeated (once) at the discretion of the investigator for any out of range results. Thereafter, laboratory tests may not be repeated unless there is a documented technical error or clinical reason to believe a result may need to be retested within the screening period

[22] regularly use known drugs of abuse and/or show positive findings on drug screening

[23] show evidence of human immunodeficiency virus (HIV) infection and/or positive HIV antibodies

[24] show evidence of hepatitis C or positive hepatitis C antibody

[25] show evidence of, or test positive for, hepatitis B and/or positive hepatitis B surface antigen and/or hepatitis B core antibody

[26] are women who are lactating

[27] have donated blood of more than 500 mL within the last month prior to dosing or intend to donate blood during the course of the study

[28] have an average weekly alcohol intake that exceeds 21 units per week (males up to age 65) and 14 units per week (females up to and over 65, and males over 65), or are unwilling to stop alcohol consumption for 48 hours prior to admission to the CRU until CRU discharge, plus 48 hours prior to admission to the CRU for the 12-week follow-up visit until final discharge from the CRU, or are unwilling to restrict alcohol intake to 3 units per day (males) and 2 units per day (females) during the outpatient period (1 unit = 12 oz or 360 mL of beer; 5 oz or 150 mL of wine; 1.5 oz or 45 mL of distilled spirits)

[29] show evidence of active or latent tuberculosis (TB), as documented by medical history and examination, any recent chest x-rays (if obtained in the previous 6 months; x-rays will not be taken for the sole purpose of determining eligibility for this study), and TB testing

- [30] had a vaccination with Bacillus Calmette-Guérin (BCG), other live vaccines, or attenuated live vaccines within 12 months prior to admission to the CRU, or intend to have a vaccination with BCG during the course of the study, or within 12 months of completing treatment in this study
- [31] have received treatment with biologic agents (such as monoclonal antibodies, including marketed drugs) within 3 months or 5 half-lives (whichever is longer) prior to dosing
- [32] intend or are likely to use over-the-counter or prescription medication for pain or inflammation within 7 days prior to dose administration. Subjects on stable doses of other medications (e.g., statins and antihypertensives) may be eligible for enrollment following discussion with the sponsor (Section 7.7)
- [33] have a known allergy or hypersensitivity to any biologic therapy that would pose an unacceptable risk to the subject if participating in this study
- [34] have had any malignancy within the past 5 years, except for basal cell or squamous epithelial carcinomas of the skin that have been resected with no evidence of metastatic disease for 3 years
- [35] have any condition that could affect pain perception from an injection
- [36] have excessive tattoos or scars over the arm, thigh, or abdomen or other factors (e.g., rash, excessive folds of skin) that, in the investigator's opinion, would interfere with injection site assessments
- [37] in the opinion of the investigator or sponsor, are unsuitable for inclusion in the study

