Izekizumab Administration			X																Subjects will fast (water is permitted) from 1 hour before until 1 hour postdose.
Izekizumab PK Sample			P	X	X	X	X	X	X	X		X		X		X	X		
Immunogenicity Sample			P					X		X							X	A time-matched PK should be taken at each immunogenicity sample time point.	
Pharmacogenetic Sample			P																
AEs and Concomitant Medication	X	X	X	X	X	X	X	X	X	X	X	X	X	X	X	X	X	If an AE of ISR is reported, the investigator or designee will complete a supplemental ISR AE form.	

Abbreviations: AE = adverse event; BMI = body mass index; CRU = clinical research unit; C-SSRS = Columbia Suicide Severity Rating Scale; d = days; ECG = electrocardiogram; ED = early discontinuation; FSH = follicle-stimulating hormone; HADS = Hospital Anxiety Depression Scale; ISR = injection site reaction; P = predose; PK = pharmacokinetics; TB = tuberculosis; TST = tuberculin skin test.

3. Introduction

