7.7. Concomitant Therapy

Subjects on stable concomitant medication at the time of study entry should continue their regular, unchanged dose throughout the study. Permitted concomitant medications, at the discretion of the investigator, include hormonal contraceptives, hormone replacement therapy, and thyroid replacement. In addition, occasional acetaminophen is acceptable at the discretion of the investigator. However, acetaminophen should not be administered on the dosing day within 4 hours prior to the injection and until at least 4 hours after the injection. No more than 3 g of acetaminophen will be permitted in any 24-hour period. Inclusion of subjects on any other concomitant medication (e.g., statins and anti-hypertensives) is contingent upon approval following consultation with the sponsor.

Subjects will be restricted from applying any creams or lotions on the arm, thigh, or abdominal skin within 24 hours prior to or after the injection.

If the need for any additional concomitant medication arises, inclusion or continuation of the subject may be at the discretion of the investigator after consultation with a Lilly Clinical

Pharmacologist (CP) or Clinical Research Physician (CRP). Any medication used during the course of the study must be documented.

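### Exclusion [30] looks back at all live vaccines but forward only at BCG, and section 7.7 has no vaccine rule to fill the gap: a minor wording correction

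*Protocol*

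**What the plan says.** Criterion [30] in Protocol section 6.2 has two parts. The look-back part covers BCG and "other live vaccines, or attenuated live vaccines within 12 months prior to admission to the CRU". The forward part reads "or intend to have a vaccination with BCG during the course of the study, or within 12 months of completing treatment in this study". The section 6.2 criteria are checked at screening and/or Day -1, and section 6 does not allow waivers.

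The remaining controls are general:

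- Criterion [37] excludes subjects who, "in the opinion of the investigator or sponsor, are unsuitable for inclusion in the study".
- Under section 7.7, if additional medication is needed, inclusion or continuation "may be at the discretion of the investigator after consultation with a Lilly Clinical" Pharmacologist or Clinical Research Physician. Inclusion of subjects on medication outside the short permitted list needs approval after sponsor consultation.
- Section 7.7 also states: "Any medication used during the course of the study must be documented".
- The Schedule of Activities (section 2) has a row for "AEs and Concomitant Medication" marked at every scheduled time point.

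Section 7.7 does set specific limits for some products. One example is "No more than 3 g of acetaminophen will be permitted in any 24-hour period"; another is a 24-hour restriction on creams and lotions around the injection. It has none for vaccines. Sections 6.3 and 8.2 and the SAP do not mention vaccines either.

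**The concern.** A subject who had a non-BCG live vaccine 11 months before admission must be excluded. A subject who plans the same vaccine two weeks after the dose meets no named exclusion, and once dosed meets no named prohibition. Whatever purpose the look-back serves, it is hard to see why it would weaken once the drug has been given.

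What is at stake is subject safety in volunteers for whom section 3.3 anticipates no therapeutic benefit. That reading is an inference. Section 6.2.1 gives only a general and non-exhaustive rationale for [9] to [37], which includes concomitant medication that may confound endpoints. The safety reading draws on three other places: [19a], which excludes subjects who "are immunocompromised to an extent such that participation in the study would pose an unacceptable risk to the subject"; [19b], which excludes known immunodeficiency; and section 9.2.1.1, which lists infection as an adverse event of special interest for ixekizumab.

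**Working it through.** The plan states no figure on this point, so the check sets the texts side by side and adds simple arithmetic for context.

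**1. Scope of [30].**

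| Part of [30] | Vaccine classes named | Period |
|---|---|---|
| Look-back | 3 (BCG, other live, attenuated live) | 12 months before CRU admission |
| Forward | 1 (BCG) | During the study and 12 months after treatment |

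**2. Comparison with a neighbouring criterion.** Criterion [27] on blood donation also has a past and a forward part. Its past part applies above a volume threshold; its forward part covers any intended donation during the study. So [27] does not narrow going forward, and [30] does, without a stated reason.

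**3. What the general clauses do after dosing.** Criterion [37] applies at entry only. Section 7.7 gives a route to sponsor consultation and requires a record. Because the exclusions are entry checks, no on-study clause forbids even BCG.

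**4. Contact frequency.** The Schedule row has 17 marks for 17 columns: Screening, Day -1, Day 1, and then Days 3, 5, 8, 11, 15, 22, 29, 36, 43, 50, 57, 64, 71 and 85, which is 14 after Day 1. Nominal gaps after Day 1 are 2, 2, 3, 3 and 4 days, then 7 days eight times (Day 15 to Day 71), then 14 days. A vaccination that the subject does not announce would be recorded within days, but after it was given.

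**5. Drug presence, for context only.** Protocol section 5.4 gives a half-life of about 13 days. With elimination only, the fraction remaining is 2^(-t/13), where t = day - 1:

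- Day 15: 2^(-14/13) = 0.474
- Day 43: 2^(-42/13) = 0.107
- Day 85: 2^(-84/13) = 0.011 (84/13 is about 6.5 half-lives)

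Allowing for first-order absorption, the share of the absorbed dose in the body is ka/(ka - ke) x (exp(-ke t) - exp(-ka t)), with ke = ln2/13. The documents give no absorption rate. Assuming an absorption half-life of 1, 2 or 4 days gives 0.513, 0.551, 0.557 at Day 15; 0.115, 0.126, 0.153 at Day 43; and 0.012, 0.013, 0.016 at Day 85. So roughly half the dose is present two weeks after injection and about 1% to 2% at the last visit. These figures describe drug presence. They do not measure vaccine risk.

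**The case against.** The strongest case is that the plan already has working controls. A subject who mentions a planned live vaccine can be refused under [37]. A need that arises later goes to the sponsor's physician or pharmacologist under 7.7. Concomitant medication is reviewed at all 17 time points. On this view only a named prohibition is missing, which is a drafting preference in a single-dose study. This stands in large part: a reader might infer that live vaccines after dosing are uncontrolled, and the documents do not support that. What does not stand is that the general clauses make the rule consistent. They allow case-by-case review, but they do not tell the site or the subject beforehand that such a vaccine should be avoided, while the look-back part of [30] is explicit.

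Second, naming BCG alone may have been deliberate. The documents do not settle this, so the asymmetry cannot be called a proven mistake.

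Third, the only purpose that section 6.2.1 names for these criteria, beyond conflict of interest, is avoiding confounded endpoints, and no effect on the endpoints is claimed here. That is fair. The wording of 6.2.1 is expressly non-exhaustive, which leaves room for a safety purpose but does not establish one.

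Fourth, a flat ban in 7.7 would turn a medically needed vaccination into a deviation, and SAP section 8 takes deviations into account when assigning subjects to populations. This is a sound objection to a bare prohibition, and the fix allows for it.

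**Conclusion.** The asymmetry is real, and [30] is the only vaccine rule in the supplied text. It is a minor point of the lowest severity: three classes named looking back, one looking forward, with general discretion and sponsor consultation in between.

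Two further inferences should be resisted. One is that the gap shows a quantified danger to subjects: the documents contain no vaccine-risk figure, and the number of subjects who might plan such a vaccine is unknown. The other is that the bioequivalence comparison is compromised: nothing in the protocol or SAP links live vaccination to ixekizumab exposure.

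The conclusion rests on the supplied text. Some protocol text between sections 3.3 and 5.1 and the consent pages were not available, and vaccine advice there cannot be ruled out. The operative sections, 6.2 and 7.7, were available.

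**What to change.** Reword the forward part of [30] along these lines: *or plan to receive BCG, another live vaccine or an attenuated live vaccine while on study, or BCG in the 12 months after treatment ends*. The existing 12-month period for BCG is unchanged.

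Add to 7.7: *Live or attenuated live vaccines, including BCG, should not be given from CRU admission through Day 85 unless medically necessary and discussed with the sponsor CP/CRP; such a vaccination does not by itself exclude the subject from the PK population.* Day 85 is the last scheduled visit, when little drug remains.

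If naming BCG alone was intended, a sentence giving the reason would also close the point.

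The cost is a wording amendment, possibly a few extra screen failures, and an occasional recorded deviation. Sampling, sample size and the PK model do not change.

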6.2.1. Rationale for Exclusion of Certain Study Candidates

Exclusion Criteria [7] and [8] prevent conflict of interest in study participants. Exclusion Criteria [9] through [37] exclude items including, but not limited to, medical conditions, medication intolerance, and concomitant medication use that may confound the assessment of study endpoints.

6.3. Lifestyle and/or Dietary Requirements

Throughout the study, subjects may undergo medical assessments and review of compliance with requirements before continuing in the study.

6.3.1. Meals and Dietary Restrictions

Subjects may receive a light meal (before dosing) on Day 1 but will be fasted (water is permitted) from 1 hour prior to dosing until 1 hour postdose. Standard meals will be provided at all other times while subjects are resident at the CRU, per the CRU's policy.

6.3.2. Alcohol and Tobacco

Alcohol consumption is not permitted while at the CRU and for 48 hours prior to each study visit. Alcohol intake during outpatient periods should not exceed 3 units per day (males up to age 65)

and 2 units per day (females up to and over 65, and males over 65). In addition, subjects must abide by the CRU smoking restrictions during study visits and while resident in the CRU.

6.3.3. *Activity*

Subjects will be encouraged to maintain their regular exercise; however, they should not undertake vigorous or prolonged exercise within 48 hours prior to each CRU visit.

6.4. Screen Failures

Individuals who do not meet the criteria for participation in this study (screen failure) may be rescreened (once) at the investigator's discretion (See Section [6](#)).

7. Treatment

7.1. Treatment Administered

A dose of IP will consist of 1 SC injection of 80-mg ixekizumab in a 1-mL volume into the arm, thigh, or abdomen. All doses will be administered by trained site staff.

This study involves a comparison of:

- 80-mg ixekizumab commercial formulation (reference) administered subcutaneously via AI
- 80-mg ixekizumab alternate formulation (test) administered subcutaneously via AI

Prior to the injection using the AI, the investigator or his/her designee will clean the subject's skin. The injection will be administered by trained site staff, according to the instructions provided by the sponsor.

[Table RHCU.3](#) shows the treatment regimens.

Table RHCU.3. Treatments Administered

Treatment Name	Alternate Formulation (Test)	Commercial Formulation (Reference)
Formulation	solution for injection	solution for injection
Dose	80-mg ixekizumab	80-mg ixekizumab
Route of Administration	SC injection	SC injection
Delivery Method	AI	AI

Abbreviations: AI = autoinjector; SC = subcutaneous.

The investigator or designee is responsible for:

- explaining the correct use of the IPs to the site personnel
- verifying that instructions are followed properly
- maintaining accurate records of IP dispensing and collection
- and returning all unused medication to Lilly or its designee at the end of the study where appropriate

Note: In some cases, sites may destroy the material if, during the investigative site selection, the evaluator has verified and documented that the site has appropriate facilities and written procedures to dispose of clinical materials. Retention samples must be kept as instructed by Lilly.

7.1.1. Packaging and Labeling

Ixekizumab will be supplied by the sponsor or its designee in accordance with current good manufacturing practice, labeled according to the country's regulatory requirements, and supplied with lot numbers, expiry dates, and certificates of analysis, as applicable. Each ixekizumab AI is

designed to deliver 80 mg of ixekizumab. The following products will be supplied by Lilly, with study-specific labels, for use in the study:

- ixekizumab commercial formulation (reference; solution for injection) in an AI (80-mg ixekizumab in a 1-mL volume)
- ixekizumab alternate formulation (test; solution for injection) in an AI (80-mg ixekizumab in a 1-mL volume)

Unblinded site personnel will be responsible for handling and administering IP. Unblinded site personnel are also responsible to make sure subjects remain blinded to treatment. Site personnel may create blinding processes and precautions as they deem necessary to maintain injection site assessor blinding.

The IP will be labeled according to the country's regulatory requirements.

7.2. Method of Treatment Assignment

The randomization table will be prepared by the statistician (or appropriate delegate) for the study and provided to the CRU pharmacists or pharmacy staff involved in dose preparation.

As described in Section 5.1, eligible subjects will be admitted to the CRU on Day -1. At screening, subjects will be stratified into 1 of 3 weight categories (<70.0 kg, 70.0 to 80.0 kg, >80.0 kg). Within the 3 weight categories, subjects will be randomized 1:1 to either 80-mg ixekizumab commercial formulation (reference) or 80-mg ixekizumab alternate formulation (test) and subrandomized 1:1:1 to injection site (arm, thigh, or abdomen) (Table RHCU.2).

7.2.1. Selection and Timing of Doses

The actual time of dose administration will be recorded in the subject's case report form (CRF).

7.3. Blinding

Study RHCU is a subject-blind study.

7.4. Dose Modification

Dose adjustments are not allowed in this study.

7.4.1. Special Treatment Considerations

All biological agents carry the risk of systemic allergic/hypersensitivity reactions. Clinical manifestations of these reactions may include, but are not limited to skin rash, pruritus (itching), urticaria (hives), angioedema (e.g., swelling of the lips and/or tongue), and anaphylactic reaction. Sometimes these reactions can be life threatening. Proteins may also cause redness, itching, swelling, or pain locally at the injection site. Therefore, all subjects should be closely monitored for signs or symptoms that could result from such reactions, be educated on the signs or symptoms of these types of reactions, and be instructed to contact the study site immediately if any of the symptoms are experienced after discharge from the CRU.

If a subject experiences an acute allergic/hypersensitivity reaction after an injection of IP, he or she should be managed appropriately and receive relevant supportive care. The event should be recorded as an AE. In case of systemic hypersensitivity reactions, defined as anaphylaxis or generalized urticaria, additional blood samples should be collected as close as possible to the onset of the event (Section 9.2.1.3). Follow-up samples should be obtained at the next regularly scheduled visit or 4 weeks after the event, whichever is later. The lab results are provided to the sponsor via the central laboratory.

